STUDY PROTOCOL AND STATISTICAL ANALYSIS

Official Title: Effectiveness of Transcranial Magnetic Stimulation on Dysphagia in Patients with Parkinson's Disease: A Randomized Double-Blind Study

Unique Protocol Id: E-70198063

Date: 22.10.2025

Our study included patients aged 40-75 years with a diagnosis of Parkinson's disease who were followed up at the Physical Medicine and Rehabilitation and Neurology outpatient clinics and who experienced dysphagia symptoms. Inclusion criteria included being followed up with a diagnosis of Parkinson's disease, moderate to severe Parkinson's disease (Hoehn-Yahr 2-4), patients describing dysphagia symptoms, and being able to give informed consent. Exclusion criteria included intracranial metallic devices, cardiac pacemakers, history of seizures, antipsychotic use, diagnosis of depression, diagnosis of dementia, findings of additional neurological disease (intracranial lesion on imaging, hydrocephalus, positive Babinski sign, cerebellar signs), and normal FEES evaluation.

A total of 129 patients followed up with a diagnosis of Parkinson's disease from the Physical Medicine and Rehabilitation and Neurology outpatient clinics were screened based on their files. Forty-one patients who met the inclusion criteria were interviewed. Six patients declined to participate in the study. Six patients experiencing dysphagia symptoms had normal FEES results. The remaining 29 patients were included in the study. After randomization, there were 14 participants in the 5 Hz group and 15 participants in the 10 Hz group. During the treatment process, one patient from the 5 Hz group and two patients from the 10 Hz group withdrew from the study for personal reasons. Thirteen patients from each group participated in the post-treatment and 9-month follow-up evaluations. The relevant study flow chart is shown in Figure 1.

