the treatment group. The TMS device used in our clinic was the Magstim Rapid 2 (Magstim Co Ltd, [name]), and a butterfly coil (D70) was used for stimulation. All treatment parameters except frequency were kept the same in both treatment groups. rTMS treatment was administered with a pulse duration of 10 seconds, an interval of 25 seconds, a total of 2000 pulses, and a stimulation intensity of 90% of the RMT of the first dorsal interosseous muscle of the hand. The current literature was reviewed when determining the treatment stimulation point. Studies conducted with stroke patients showed that 4-6 cm lateral and 2-4 cm anterior to the vertex were used for mylohyoid cortex stimulation. (17-20) The study referenced by all these studies is the one conducted by Khedr et al., in which the cortical topography of the swallowing muscles was mapped. (21) In our study, the vertex point was determined according to the international 10-20 method. Subsequently, based on the existing literature, 6 cm lateral and 3 cm anterior to the vertex point was determined as the mylohyoid and pharyngeal cortex stimulation point. Both groups were given cervical strengthening, shaker, massako exercises, and triflo breathing exercises as home exercises. After 10 sessions of rTMS treatment, the patients underwent a second evaluation, and the scores from the first evaluation were used.

After rTMS treatment, patients were asked to continue swallowing exercises. They were called for a follow-up evaluation at 9 months. The same evaluations performed at the first and second visits were also performed at the third visit.

G-Power software was used to calculate the sample size. According to the ANOVA analysis, the significance value was $p<0.05$; the effect size was 0.30, and the minimum sample size was calculated as 26 at a 95% confidence interval.

The statistical analysis of the study was performed using IBM SPSS Statistics version 27.0 and R analysis version 4.5.0. Descriptive statistical methods were used to examine demographic data. The normality of data distribution was assessed using the Shapiro-Wilk test. Since the data were found to be non-normally distributed, non-parametric tests were used.

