The “Cochran test” and “Brunner Langer test” were used to evaluate the time-dependent distribution of categorical data within groups, and the “Dunn Bonferroni test” was used for pairwise comparisons of significant data. The “Chi-square test” was used for the intergroup evaluation of categorical data. The Friedman test was used to evaluate the time-dependent change in numerical data within groups, and the Mann-Whitney U test was used for the intergroup evaluation. The correlation of pre-treatment parameters was evaluated using Spearman correlation analysis.

The statistical significance level was set at $p<0.05$.

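### For two-level items at 13 per arm, the unspecified between-arm chi-square test either exceeds 5% (up to 7.6%, uncorrected) or is conservative (at most 2.9%, continuity-corrected)

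*Combined protocol and SAP*

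**What the plan says.** The closing statistical analysis paragraphs of the combined protocol and SAP assign the between-arm comparison of categorical data to a single method: the chi-square test "was used for the intergroup evaluation of categorical data". They do not say whether a continuity correction applies, when an exact test would replace it, or what happens when expected counts are small. The analysis used both SPSS 27.0 and R 4.5.0, and the text does not fix the form of the test in either.

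For change over time, the Cochran and Brunner-Langer tests "were used to evaluate the time-dependent distribution of categorical data within groups". The Cochran test takes two-level data, so some two-level items are evidently analysed, although none is named.

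On the threshold: "The statistical significance level was set at" p<0.05.

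On numbers, the participant-flow paragraph says "Thirteen patients from each group participated in the post-treatment and 9-month follow-up evaluations". At randomisation "there were 14 participants in the 5 Hz group and 15 participants in the 10 Hz group".

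**The concern.** The chi-square test relies on a large-sample approximation. With 13 per arm a two-level item can give only 14 x 14 = 196 outcomes, so the real chance of a false positive moves in steps and need not be close to 5%. The form of the test is also left open, and the two usual forms err in opposite directions.

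The contrast of 5 Hz with 10 Hz is the only randomised comparison in the trial. With the uncorrected form, a difference on a yes/no item could be declared when exact evidence does not support it at 5%. With the corrected form, a real difference is more likely to be missed than it need be. The same data, such as 9 of 13 v 4 of 13, would be reported as significant under one form and not under the other.

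**Working it through.** **Inputs.** n = 13 per arm (participant flow, post-treatment and 9 months). Nominal level 0.05 (statistical analysis). A 2 x 2 chi-square with 1 df is two-sided by construction; its critical value is 3.841. The documents give no event rate, so the common rate p is varied over its whole range.

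**Test statistic.** With a events in one arm, c in the other and m = a + c, the chi-square at 13 v 13 reduces to

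X² = 26(a − c)² / [m(26 − m)],

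and the continuity-corrected form replaces |a − c| by |a − c| − 1. For 9 v 4:

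- Uncorrected: 26 × 25 / (13 × 13) = 650/169 = 3.846, p = 0.0499, significant.
- Corrected: 26 × 16 / 169 = 416/169 = 2.462, below 3.841, not significant.

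**True level.** For each p, sum Bin(a; 13, p) × Bin(c; 13, p) over the outcomes that the test rejects. The figure to reproduce is the plan's 5%.

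| Common rate | 10% | 20% | 25% | 30% | 40% | 50% | Maximum |
|---|---|---|---|---|---|---|---|
| Uncorrected | 1.8% | 4.3% | 5.0% | 5.65% | 7.0% | 7.56% | 7.56% |
| Corrected | 0.3% | 1.4% | 1.8% | 2.1% | 2.6% | 2.9% | 2.90% |

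Neither form delivers 5% across the range. The uncorrected test is above 5% from about 26% to 74%. At 13 v 13 Fisher's exact test rejects exactly the same tables as the corrected chi-square, so its maximum is also 2.90%. The common working rule (Fisher when any expected count is below 5, otherwise uncorrected) has a maximum of 6.6% and exceeds 5% for rates of about 39% to 61%. At the randomised sizes, 14 v 15, the maxima are 6.2% uncorrected and 2.4% corrected.

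**Where the tests disagree.** The smallest expected count is min(m, 26 − m)/2.

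| Split (of 13 each) | X² uncorrected | Fisher p | Boschloo p | Smallest expected |
|---|---|---|---|---|
| 4 v 0, 13 v 9 | 416/88 = 4.727 | 0.096 | 0.040 | 2.0 |
| 6 v 1, 12 v 7 | 650/133 = 4.887 | 0.073 | 0.032 | 3.5 |
| 7 v 2, 11 v 6 | 650/153 = 4.248 | 0.097 | 0.0485 | 4.5 |
| 8 v 3, 10 v 5 | 650/165 = 3.939 | 0.111 | 0.061 | 5.5 |
| 9 v 4 | 650/169 = 3.846 | 0.115 | 0.076 | 6.5 |

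All nine splits are significant uncorrected and not significant by Fisher. Under Boschloo only the last two rows (three splits) lose significance. Those are also the ones that a check for expected counts below 5 does not catch.

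**Hand check of the excess at p = 50%**, where every pair of sequences has probability 1/2²⁶ = 1/67,108,864:

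- 8 v 3 and its mirror: 2 × 1287 × 286 / 67,108,864 = 1.10%. For 10 v 5: 2 × 286 × 1287 gives the same 1.10%.
- 9 v 4 and its mirror: 2 × 715 × 715 / 67,108,864 = 1.52%.
- Total 3.72%. Removing it leaves 7.56% − 3.72% = 3.84%.

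So these three splits account for the whole breach at 50%. Over all common rates Boschloo's maximum level is 4.85%.

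**Power at 20% v 60%:** uncorrected 63%, Boschloo 54%, Fisher or corrected chi-square 46%.

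**The case against.** The strongest reply is about relevance. The named assessments (FOIS, FSS, EAT-10, two residue scales and the penetration aspiration scale) are all described as scored scales or tests, none as a yes/no item. Two-level items are inferred from the Cochran test alone and might be minor entries on the swallowing assessment form. Nothing shows that a treatment conclusion rests on one. This stands, and it limits the weight of the point.

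Second, 7.6% is a worst case. For rates at or below 25%, or at or above 75%, the uncorrected test stays within 5%, and averaged evenly over all rates its level is 4.5%. This also stands. The documents give no rate that would place an item inside or outside the affected band.

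Third, a reader might infer that the corrected version also fails to hold 5%. It does not fail: a maximum of 2.9% is control of the level, and the cost is in power.

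Fourth, a reader might infer that all nine splits in the table are false findings. Six of them (4 v 0, 6 v 1, 7 v 2, 11 v 6, 12 v 7, 13 v 9) disagree only with Fisher. Boschloo keeps them significant, and each has an expected count below 5, so the usual check would already flag them.

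Finally, Boschloo is one acceptable choice among several. Stating the form of the test is the minimum; Fisher would also be valid, at the power cost shown.

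**Conclusion.** The point holds in a limited form. For two-level items at 13 v 13, the plan's threshold of p<0.05 is not the error rate delivered. Uncorrected, the level exceeds 5% for common rates of about 26% to 74%, by at most 2.6 percentage points (7.56% − 5% = 2.56). Corrected, the level is controlled but never exceeds 2.9%, and power at 20% v 60% is 8 points below Boschloo (54% − 46%). Because the plan does not say which form was used, 8 v 3, 9 v 4 and 10 v 5 could be reported either way.

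This rests on independent binomial outcomes in the two arms, two-sided testing, 13 per arm, and the inference that two-level items exist. The documents do not show that any particular reported result is wrong. The calculation does not cover items with more than two levels, nor which test suits ordered scales.

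**What to change.** In the statistical analysis paragraph, replace the chi-square test for between-arm comparisons of two-level items with Boschloo's exact unconditional test, list the items to which it applies, and re-run any such result already obtained. If the chi-square is retained for any two-level item, state whether it is continuity-corrected.

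The cost is one sentence and a re-run in R, which the study already uses. Relative to the uncorrected chi-square, results at 8 v 3, 9 v 4 and 10 v 5 (and mirror images) lose significance, and power at 20% v 60% falls from 63% to 54%. Relative to the corrected chi-square or Fisher, power at the same rates rises from 46% to 54%.

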Patient files were scanned through the hospital system, and patients who met the inclusion criteria for the study were contacted by telephone. During this conversation, patients were informed about the content, purpose, duration, and possible complications of the study. Patients who agreed to participate in the study were invited for an examination. During this examination, patients were assessed for the presence of exclusion criteria. For patients deemed suitable for participation, the swallowing assessment form, FOIS, FSS, and EAT-10 test were completed. This was followed by a flexible endoscopic swallowing evaluation (FEES). During this evaluation, the YALE-2016 valeric residue scale, YALE-2016 piriform sinus residue scale, and penetration aspiration scale were scored. Participants were then assigned to one of two treatment groups.

Randomization was performed using a computer program. Treatments were administered at 5 Hz to one group and 10 Hz to the other group. Treatments consisted of a total of 10 sessions over two weeks, applied bilaterally to the pharyngeal and mylohyoid cortex by another researcher. Neither the researchers performing the assessments nor the patients were aware of

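### The 5 Hz v 10 Hz comparison leaves the pre-randomisation scores unused and does not say which visit or variable it tests

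*Combined protocol and SAP*

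**What the plan says.** The combined protocol and SAP has no numbered sections. The points below come from its statistical-methods text and its accounts of assessment and follow-up.

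- **Tests over time.** For categorical data, the Cochran and Brunner-Langer tests "were used to evaluate the time-dependent distribution of categorical data within groups". For numerical data, the Friedman test covers "time-dependent change in numerical data within groups, and the Mann-Whitney U test was used for the intergroup evaluation".
- **Tests between arms.** Mann-Whitney is used for numerical data, as just quoted. The chi-square test "was used for the intergroup evaluation of categorical data".
- **Choice of method.** "Since the data were found to be non-normally distributed, non-parametric tests were used".
- **Timing of baseline.** "For patients deemed suitable for participation, the swallowing assessment form, FOIS, FSS, and EAT-10 test were completed". The endoscopic evaluation and its three scales came next, and only after that: "Participants were then assigned to one of two treatment groups".
- **Later visits.** After the ten sessions "the patients underwent a second evaluation, and the scores from the first evaluation were used". At 9 months, "The same evaluations performed at the first and second visits were also performed at the third visit".

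No part of the document names the visit, the form of the variable or a baseline covariate for the comparison between arms. The only other use of baseline values is a Spearman correlation among pre-treatment measures, which adjusts nothing. Thirteen patients per arm attended both later visits.

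**The concern.** The randomised question is whether 5 Hz and 10 Hz differ. As described, every test that uses the repeated measurements looks inside one arm, and the tests that compare the arms ignore baseline. Two things are at stake.

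**Precision.** Each scale was scored before assignment, so its baseline value is a legitimate covariate that is already in hand. With 13 per arm, chance baseline differences are common. A raw follow-up comparison carries such a difference forward, and a change-score comparison over-corrects for it. Which of the two loses less depends on a correlation that the documents do not give.

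**Interpretation.** With two later visits and two possible variables, a reader cannot tell what a between-arm p-value refers to. Separate within-arm p-values also invite a contrast between arms that they cannot support.

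**Working it through.** **The plan's own figure.** The minimum sample of 26 cannot be reproduced from its stated inputs (ANOVA, effect size 0.30, p<0.05), because power, type of ANOVA and correlation are missing. One match is a three-visit repeated-measures ANOVA (within-subject or interaction) with assumed correlation 0.5: noncentrality = f²·N·m/(1−ρ) = 0.09 × 26 × 3 / 0.5 = 14.04, giving power 0.91. The match cannot tell a time effect from an arm-by-visit effect, so it does not settle which comparison was meant. Nothing below depends on it.

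**Inputs.** From the documents: 13 v 13, three visits, 0.05 level. Assumed: two-sided tests, normal data, equal correlation r between visits of 0.3, 0.5 or 0.7, and a 0.6 SD difference at both later visits. The 0.6 is illustrative; it equals 2 × 0.30, but the plan does not tie its 0.30 to a contrast between arms.

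**Step 1: why adjustment helps.** The effective standardised effect is:

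| Analysis | Formula | r = 0.3 | r = 0.5 | r = 0.7 |
|---|---|---|---|---|
| Raw score | 0.6 | 0.60 | 0.60 | 0.60 |
| Change | 0.6/√(2(1−r)) | 0.51 | 0.60 | 0.77 |
| Baseline-adjusted | 0.6/√(1−r²) | 0.63 | 0.69 | 0.84 |

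The adjusted analysis is the largest in each column. Raw beats change at 0.3, ties at 0.5 and loses at 0.7.

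**Step 2: power of the rank tests.** Simulation, one visit, no Holm, Mann-Whitney without continuity correction so that all three tests have error near 5%:

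| Test | r = 0.3 | r = 0.5 | r = 0.7 |
|---|---|---|---|
| Rank ANCOVA | 0.31 | 0.36 | 0.47 |
| Mann-Whitney, raw | 0.30 | 0.30 | 0.30 |
| Mann-Whitney, change | 0.23 | 0.30 | 0.45 |
| Gain over the better Mann-Whitney | 0.01 | 0.06 | 0.02 |

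With the continuity correction, raw Mann-Whitney falls to 0.28, which would overstate the gain.

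**Step 3: error with no true difference, one visit.** With continuity correction, Mann-Whitney rejects in 4.2-4.4% (raw) and 4.3-4.6% (change) of trials. Rank ANCOVA rejects in 5.0-5.2%.

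**Step 4: error when baseline happens to be unbalanced.** A baseline difference of at least 0.5 SD has probability 2·P(Z > 0.5/√(2/13)) = 2·P(Z > 1.275) = 0.20. Among those trials, at one visit with no true difference (continuity-corrected Mann-Whitney), error at r = 0.3 / 0.5 / 0.7 is:

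- raw: 6.0 / 9.3 / 13.3%
- change: 10.8 / 9.3 / 7.7%
- rank ANCOVA: 5.2 / 5.2 / 5.8%

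A repeat run agreed to within about one percentage point (change 11.9% at 0.3). In round terms this is 6-13%, 8-12% and 5-6%.

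**Step 5: error over the two visits of one scale.** Chance of at least one false positive:

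| Test | No Holm | Holm |
|---|---|---|
| Mann-Whitney, raw | 7-8% | about 4% |
| Rank ANCOVA | about 10% | about 5% |

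Control across visits comes from Holm, not from the covariate.

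**Step 6: within-arm p-values.** With the same true change in both arms (0.3 to 1.0 SD, correlation 0.5), Friedman was significant in exactly one arm in 24-48% of simulated trials. Mann-Whitney on change stayed at 4-5%.

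**The case against.** **The listed tests are valid.** This stands. Randomisation protects an unadjusted Mann-Whitney comparison, and its overall error is at or just below 5% per visit. A reader might infer from step 4 that the results are biased. That would be wrong: those rates apply only to the one trial in five with a marked chance imbalance, and no document reports such imbalance here.

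**An arm-by-visit test may exist.** This also stands. The Brunner-Langer method covers factorial longitudinal designs and can include an arm factor. The text describes it as within-arm and for categorical data, but that may be loose wording. The supportable statement is that no interaction is reported in the plan, not that none was run.

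**A test chosen after the data should not displace a stated one.** Agreed. Follow-up is complete and the data have been checked for normality. Making rank ANCOVA the single deciding analysis would add an analytic choice. It belongs beside Mann-Whitney.

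**The gain is small.** Partly right: it is 0.01-0.02 at correlations 0.3 and 0.7 against the better Mann-Whitney variant. But which variant is better depends on the correlation. Against raw scores alone, the gain at 0.7 is 0.47 − 0.30 = 0.17. Rank ANCOVA was at least as powerful as either variant at each correlation tried.

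**No passage uses within-arm p-values to compare arms.** True, so that part is a caution for reporting.

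**Conclusion.** The point holds as a modest, nearly free improvement. As described, the plan's comparison between arms omits baseline scores collected before assignment and does not identify its visit or variable. The phrase about first-evaluation scores being used after treatment does not settle this; it may mean only that the same scales were repeated.

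The gain in power at one visit is about 0.01 to 0.06 over the better Mann-Whitney variant, with better protection if baseline was unbalanced by chance. These figures rest on normal data, assumed correlations of 0.3-0.7 and an assumed 0.6 SD effect. Power stays below one half in every setting of step 2.

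A reader might also infer selective reporting from the open choice of visit and variable. The documents give no sign of it; the text simply lacks the detail. Nor should rank ANCOVA be credited with controlling error over two visits, as step 5 shows.

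**What to change.** 1. For each ordinal or numerical scale, add a rank ANCOVA (ranked post-baseline score on arm and ranked baseline score) after treatment and at 9 months. Report it for every scale and both visits, beside the listed Mann-Whitney test, and label it post hoc.
2. Apply Holm across the two visits to both methods alike: the smaller p-value against 0.025 and, if that is met, the larger against 0.05.
3. State the visit and the variable for each Mann-Whitney and chi-square test.
4. Say whether Brunner-Langer included an arm factor. If it did, report the arm-by-visit interaction as supportive.
5. Base no conclusion about 5 Hz v 10 Hz on within-arm p-values.

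The cost is a re-run in R, which the study already uses, and some wording. No patients or data are added. The downsides are a few more analyses, a post hoc label, power that remains low at 0.6 SD, no adjusted analysis for binary outcomes, and no control of error across the several scales.

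### No primary scale or visit is named and between-arm tests on six scales are unadjusted: the chance of a false 5 Hz versus 10 Hz result is about 16–26% (6 tests) or 23–46% (12 tests), at assumed correlations of 0.7 down to 0

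*Combined protocol and SAP*

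**What the plan says.** The document has no numbered sections, so places are given by subject.

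- **Assessments.** At the first visit "the swallowing assessment form, FOIS, FSS, and EAT-10 test were completed". At the endoscopy two Yale residue scales and the penetration aspiration scale were scored ("piriform sinus residue scale, and penetration aspiration scale were scored"). That makes six named scales: FOIS, FSS, EAT-10, two residue scales and the penetration aspiration scale. The swallowing assessment form is listed but not described as scored.
- **Visits.** There is an evaluation after the 10 sessions and another at 9 months: "The same evaluations performed at the first and second visits were also performed at the third visit". On numbers: "Thirteen patients from each group participated in the post-treatment and 9-month follow-up evaluations".
- **Sample size.** An ANOVA in G-Power is cited: "the effect size was 0.30, and the minimum sample size was calculated as 26". No outcome, visit, contrast or power is given.
- **Between-arm tests.** Chi-square is assigned to categorical data. For numerical data, "the Mann-Whitney U test was used for the intergroup evaluation". The text does not say which scales fall in which class.
- **Adjustment.** Dunn–Bonferroni "was used for pairwise comparisons of significant data", in the sentence on change over time within groups.
- **Threshold.** "The statistical significance level was set at" p<0.05, without qualification.

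**The concern.** The arms differ only in stimulation frequency, so 5 Hz versus 10 Hz is the question the randomisation was meant to answer. The plan gives no rule for which result answers it. Any of six scales, at either of two post-baseline visits, could be put forward, each judged at 0.05 on its own. The text also leaves open whether each scale is compared between arms once or at both visits.

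An isolated p<0.05 on one scale at one visit is then fairly likely by chance, and nothing in the plan would stop it being reported as evidence that one frequency is superior.

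**Working it through.** **Does the sample size identify a deciding comparison?** The document gives effect size f = 0.30, α = 0.05 and N = 26, but no power, correlation or type of ANOVA. For a repeated-measures within-patient or group-by-time test with m = 3 visits, g = 2 groups and an assumed correlation ρ = 0.5:

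- noncentrality λ = N f² m/(1−ρ) = 26 × 0.09 × 3/0.5 = 14.04, on 2 and 48 degrees of freedom, which gives power 0.912;
- the smallest even N is 20, 26 and 32 at power 0.80, 0.90 and 0.95.

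A between-group repeated-measures effect would need 62, 80 and 100, and a one-way ANOVA 90, 120 and 148. So 26 can be reached with assumed settings (power 0.90, ρ = 0.5, three visits) but cannot be confirmed from what is stated. On no reading does it point to a particular scale or visit. The results below do not depend on it.

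**Inputs for the error rate.**
- α = 0.05 per test, from the statistical analysis paragraph. Two-sided testing is assumed.
- k = 6 if each scale is compared between arms once, or 6 × 2 = 12 if at both post-baseline visits. Baseline comparisons are left out.
- 13 patients per arm.
- Common correlation ρ between test statistics: not in the document, so varied from 0 to 0.9.

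**Formulas.** With independent tests the chance of at least one false positive is 1 − 0.95^k:
- k = 6: 1 − 0.95⁶ = 0.265
- k = 12: 1 − 0.95¹² = 0.460

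For ρ > 0 and c = 1.96, it is 1 − ∫ φ(u) [Φ((c − √ρ u)/√(1−ρ)) − Φ((−c − √ρ u)/√(1−ρ))]^k du, evaluated numerically.

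**Results.** The Mann–Whitney rows are simulations of 20,000 runs, tie-corrected, with 13 per arm and assumed skewed ordinal scores of 5 to 12 levels.

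| | ρ = 0 | 0.3 | 0.5 | 0.7 | 0.9 |
|---|---|---|---|---|---|
| 6 tests, formula | 26.5% | 24.1% | 20.7% | 16.4% | 10.8% |
| 6 tests, Mann–Whitney | 25.6% | 24.3% | 21.5% | 17.7% | 12.6% |
| 12 tests, formula | 46.0% | 39.7% | 31.9% | 23.2% | 13.5% |
| 12 tests, Mann–Whitney | 45.0% | 40.3% | 34.0% | 26.3% | 16.4% |

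If the correlation is 0.7 between scales and 0.7 between visits, multiplying across the two, 12 tests give about 26% instead of 23%.

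**With a divided threshold.** At 0.05/6 = 0.0083 or 0.05/12 = 0.0042, the chance is at most 4.9% in every case by formula. In the Mann–Whitney simulation it is at most 4.1% (6 tests) and 3.8% (12 tests).

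**The case against.** **The percentages are illustrative.** The document gives no correlations, and independence is unlikely for related scales repeated in the same 26 patients, so 26% and 46% are upper ends. This stands. But the chance stays at two or more times the nominal 5% even at correlation 0.9.

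**Some scales may be tested by Chi-square, which is conservative in small sparse tables.** This also stands in part. Simulations in which some scales were tested by Chi-square, under assumed distributions, gave about 15–21% for 6 tests and 29–39% for 12. The top of each range falls, and the conclusion does not change.

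**The number of tests is inferred.** True: the text does not say that every scale was compared at every visit, nor whether scores or changes were used. That is why both 6 and 12 are shown.

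**A primary outcome may be recorded elsewhere.** Possibly. The claim is only that this document names none, and the remedy allows for one fixed in advance.

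**A 26-patient study can reasonably be exploratory, and the document makes no superiority claim.** Reporting every between-arm result as exploratory, with no claim that one frequency is better, would be defensible. The document does not take that course: it describes a randomised double-blind study of effectiveness and applies p<0.05 throughout.

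**Conclusion.** The concern holds. As written, the plan neither names a deciding between-arm comparison nor controls error across the several it allows. With no true difference, the chance of at least one nominally significant 5 Hz versus 10 Hz result is about 16–26% for 6 tests and 23–46% for 12, over correlations of 0.7 down to 0. At correlation 0.9 it is 11% and 13%.

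These figures assume two-sided tests, one common correlation, and one or two post-baseline comparisons per scale. The finding that error is uncontrolled rests on the text alone. It does not invalidate the data, but an isolated claim of superiority would lack error control. The sponsor should correct it.

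**What to change.** 1. If a primary scale and visit were fixed before any data were seen, state them, say where and when that was recorded, and test that single between-arm comparison at 0.05.
2. If not, choose neither now. The text is in the past tense and reports completed 9-month follow-up, so a choice at this stage could be driven by the data. Apply Holm across all between-arm post-baseline tests actually run, including any Chi-square tests. The smallest p-value is compared with 0.05/12 = 0.0042 if 12 were run, or 0.05/6 = 0.0083 if 6. Holm is valid under any correlation, so it does not depend on the values assumed above.
3. State how many between-arm tests were run, and disclose with a date that the adjustment was added after the analysis.
4. Label the within-arm tests and the correlations exploratory, and draw no claim from them that one frequency is superior.

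**Cost.** Adjusted p-values from tests already run and a dated disclosure; no new data. Fewer results will be called significant. With 13 per arm and 80% power (t-test approximation), the detectable difference is 1.15 SD at 0.05, 1.47 SD at 0.0083 and 1.59 SD at 0.0042.
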